5 STUDY METHODOLOGY

5.1 Efficacy Outcomes

The primary endpoint will be the composite of death or the need for hospitalization due to COVID-19 infection in the first 30 days after randomization. The secondary endpoints will consist of the components of the composite primary endpoint; and the need for mechanical ventilation in the first 30 days after randomization. Exploratory endpoints will include associations between senescent biomarkers and long hauler syndrome effects.

Biomarkers endpoints:

Samples received from participants will be kept frozen until evaluation of biomarkers. Samples will be stored and processed at Mayo Clinic Rochester.

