OUTCOMES: The primary endpoint will be the rate of complications related to COVID-19 (CoV) disease using a 7 point score adapted from the WHO Ordinal Scale for Clinical Improvement of CoV (Appendix A) in the 30 days following randomization. The secondary endpoint is to determine safety and tolerability of treatment with Fisetin in this patient population. Exploratory objectives are to evaluate links between soluble and genetic markers of senescent cell abundance, SASP factors, inflammation, viral load, and treatment effects and if Fisetin treatment during acute CoV infection decreases Long-hauler syndrome at Days 60.

STATISTICAL RATIONALE AND ANALYSIS: All main analyses in COVFIS-HOME will be conducted on an intention-to-treat basis. Assuming 75 subjects/ group with a significance level of 0.05, the study will have 80% power to detect an odds ratio of 2.24 comparing the placebo- to Fisetintreated group, using the 7-point severity score at Day 30 as the endpoint in an ordinal logistic regression model.

A fully independent 5-member Data and Safety Monitoring Board (DSMB) will be established and will review unblinded safety data as detailed in the DSMB charter. An interim analysis is planned after approximately 50% of randomized patients have completed 30 days of follow-up.

The DSMB charter will pre-specify the methods of interim efficacy analyses and the rules for early study termination, approved by all board members. The stopping rules for efficacy will be based on the O'Brien-Fleming α -spending function or on a similar conservative approach so that the impact on the final alpha level will be negligible. Futility will be assessed by computing conditional power. The DSMB will have the option of recommending early study termination because of overwhelming efficacy, early termination for futility, or continuation of the trial as planned.

The primary analysis of efficacy will be based on the intent-to-treat principle. The primary endpoint will be compared between the two treatment groups using a chi-square test. Secondary endpoints will be analyzed similarly.

ANTICIPATED TOTAL NUMBER OF RANDOMIZED PATIENTS: Approximately 150 patients in total will be randomized in this study.

STUDY LOCATION: Mayo Clinic Minnesota.

GLOSSARY

AE Adverse Event/Adverse Experience

AFFIRM Alleviation by Fisetin of Frailty, Inflammation, and Related Measures Trial

ALT Alanine Aminotransferase

ARDS Acute Respiratory Distress Syndrome

AST Aspartate Aminotransferase

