The target of senolytics is senescent cells, not a single receptor, enzyme, or biochemical pathway. By targeting pro-survival networks instead of single molecules, specificity for senescent cells can be increased, side-effect profiles flattened, and off-target effects on non-senescent cells reduced. Drugs that have single or limited targets, such as Navitoclax (ABT-263), which we discovered is senolytic at the same time as another group 46,47, or Nutlin3a, have off-target apoptotic effects on multiple non-senescent cell types, making them "panolytic". Navitoclax, a BCL-2/ BCL-w/ BCL-xL inhibitor, eliminates only a restricted range of senescent cells, *e.g.*, BCL-2 inhibitors are not senolytic against human adipocyte progenitors, one of the most abundant senescent cell types in aged humans or people with diabetes and obesity. Our strategies for developing senolytics have more in common with approaches for developing antibiotics than the conventional one-target/one-drug/one-disease drug development approach.

Description of the population to be studied. Adult women and men with PCR positive SARS-CoV-2 infection, will be screened for inclusion in this study. Subjects who meet screening criteria will be randomized to receive Fisetin 20 mg/kg/day orally (capsules or powder dissolved in water or added to apple sauce, pudding, or yogurt) or by nasogastric (NG-tube) or transabdominal duodenal tube (D-tube; powder dissolved in water within 30 minutes, to achieve transient, high tissue Fisetin levels in a "hit-and-run" approach or placebo for 2 days (Days 0-1 and 8-9) and will be followed until study Day 30 or death. Subjects will continue to be followed for 2 months. The primary outcome is need for hospitalization and death with COVID-19. Secondary outcomes will be assessment for long hauler syndrome. Buccal swabs, urine and stool tests will be conducted before and after initiating treatment with Fisetin or placebo serially.

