2 STUDY OBJECTIVES

The primary objective of this study is to determine whether short-term treatment with Fisetin reduces

the rate of complications related to COVID-19 (CoV) disease using a 7 point score adapted from the WHO Ordinal Scale for Clinical Improvement of CoV (Appendix A). The secondary objective is to determine safety and tolerability of treatment with Fisetin in this patient population. Exploratory objectives are to evaluate links between soluble and genetic markers of senescent cell abundance, SASP factors, inflammation, viral load, and treatment effects.

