8 DATA ANALYSIS AND STATISTICAL CONSIDERATIONS

8.1 Statistical Power and Sample Size Considerations

All main analyses in COVFIS-HOME will be conducted on an intention-to-treat basis. Assuming 75 subjects/ group with a significance level of 0.05, the study will have 80% power to detect an odds ratio of 2.24 comparing the placebo- to Fisetin-treated group, using the 7-point severity score at Day 30 as the endpoint in an ordinal logistic regression model.

Analysis population

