8.2 Data analysis

8.2.1 Analysis of efficacy outcomes

The primary analysis of efficacy will be based on the intent-to-treat principle. The primary endpoint will be compared between the two treatment groups using a chi-square test. Logistic regression models might also be used to compare the primary endpoint between the two treatment groups while accounting for important baseline characteristics. Secondary endpoints will be analyzed similarly. Exploratory analysis (biomarkers) will include logistic regression models with the primary/secondary endpoints as dependent variables and with treatment group, biomarker and treatment group x biomarker interaction as independent variables.

All statistical tests will be two-sided and conducted at the 0.05 significance level, with the exception of the primary analysis that will be conducted at a slightly lower level to account for the interim analysis. Statistical analyses will be done using SAS version 9.4 or higher.

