8.2.3 Interim analysis

A fully independent 5-member Data and Safety Monitoring Board (DSMB) will be established and will review unblinded safety data as detailed in the DSMB charter. An interim analysis is planned after approximately 50% of randomized patients have completed 30 days of follow-up. The DSMB charter will pre-specify the methods of interim efficacy analyses and the rules for early study termination, approved by all board members. The stopping rules for efficacy will be based on the O'Brien-Fleming alpha-spending function or on a similar conservative approach so that the impact on the final alpha level will be negligible. Futility will be assessed by computing conditional power. The DSMB will have the option of recommending early study termination because of overwhelming efficacy, early termination for futility, or continuation of the trial as planned.

The final analysis of the primary endpoint will be conducted at a significance level slightly below

the 0.05 level to account for the interim analysis. However, since this will have a negligible impact on power, the sample size calculation was calculated using a significance level of 0.05.

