3.6 Other Adverse Events

Study endpoints are to be reported in the eCRF within 24 hours of awareness of the event.

In addition to SAEs and study endpoints, the only AEs to be recorded on the eCRF are those that are either related to the gastrointestinal system, that are judged related to the study medication by the investigator or that are laboratory abnormalities judged clinically significant by the investigator. Information collected will include the onset, duration, severity, relationship to study drug, and the management.

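### The plan names two different primary endpoints, a 7-point score and a binary death-or-hospitalization composite, and the chi-square test it specifies is not the ordinal model it was powered for

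*Combined protocol and SAP*

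**What the plan says.** Two descriptions of the primary endpoint stand in current text.

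- **Ordinal score.** The synopsis (Outcomes) says "The primary endpoint will be the rate of complications related to COVID-19 (CoV) disease using a 7 point score adapted from the WHO" scale, over the 30 days after randomization. Section 2 frames the primary objective as "the rate of complications related to COVID-19 (CoV) disease using a 7 point score adapted from the WHO Ordinal Scale".
- **Binary composite.** Section 5.1 says "The primary endpoint will be the composite of death or the need for hospitalization due to COVID-19 infection" within 30 days of randomization. The description of the study population in Section 1.1 agrees: "The primary outcome is need for hospitalization and death with COVID-19".

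The synopsis objective adds a third wording, death and long-term complications. The secondary endpoints differ too: safety and tolerability in the synopsis, but the components of the composite plus mechanical ventilation in Section 5.1.

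On analysis, the synopsis and Section 8.1 claim 80% power for an odds ratio of 2.24 with 75 per group at the 0.05 level, "using the 7-point severity score at Day 30 as the endpoint in an ordinal logistic regression model". The synopsis and Section 8.2.1 then say: "The primary endpoint will be compared between the two treatment groups using a chi-square test". Section 8.2.1 also allows logistic regression with baseline covariates as an option. For the interim look, Section 8.2.3 says: "The DSMB charter will pre-specify the methods of interim efficacy analyses and the rules for early study termination".

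**The concern.** A seven-level score and a yes/no composite are different variables. They could be linked by cutting the score at a chosen level, but no section does this. Nor does the synopsis explain how a score becomes a rate.

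Timing differs as well. A score at Day 30 describes a patient's state on that day; the composite collects events over the whole 30 days. A patient admitted in the first week and well by Day 30 is an event on the composite but can have a good Day 30 score. The two endpoints can therefore lead to different conclusions from the same patients.

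The test is a second mismatch. A chi-square test suits the composite. On a seven-level score it ignores the ordering that the power calculation relies on.

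Three things are at stake: the primary p-value depends on a choice that could be made after data are seen; the interim efficacy and futility rules have no single endpoint to refer to; and the stated 80% power may not belong to the analysis that is run.

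**Working it through.** **Inputs from the documents.** 75 per group and 1:1 allocation (Sections 3.3, 8.1); odds ratio (OR) 2.24, 80% power, alpha 0.05 (Section 8.1); two-sided tests (Section 8.2.1). No placebo event rate or category distribution is given, so every rate and distribution below is an assumption.

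**1. The plan's own figure.** Whitehead's proportional-odds formula for 1:1 allocation is

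N = 12 (z₀.₉₇₅ + z₀.₈₀)² / [(ln OR)² (1 − Σp̄ᵢ³)],

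where p̄ᵢ is the mean proportion in category i over the two arms. Here (1.960 + 0.842)² = 7.849 and (ln 2.24)² = 0.6504. With seven equal categories, 1 − Σp̄ᵢ³ = 1 − 7/343 = 0.9796, so N = 12 × 7.849 / (0.6504 × 0.9796) = 147.8, against 150 planned. Power at N = 150 is 80.6%. If only the placebo arm is evenly spread and Fisetin is shifted by OR 2.24, power is 80.4%. The stated 80% therefore reproduces, as a two-sided figure for an ordinal model with a nearly even spread. The interim look does not disturb this: a Lan-DeMets O'Brien-Fleming boundary with one look at 50% leaves a final alpha of about 0.0478 and power of 80.0%.

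**2. If Section 5.1 governs.** With placebo rate p₀, the Fisetin odds are p₀/(1 − p₀)/2.24. Power comes from exact enumeration of the uncorrected chi-square test with 75 per arm; the last column uses the pooled-variance sample size formula.

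| Placebo rate (assumed) | Fisetin rate at OR 2.24 | Exact power | n per arm for 80% |
|---|---|---|---|
| 5% | 2.3% | 12.8% | 754 |
| 10% | 4.7% | 24.1% | 384 |
| 15% | 7.3% | 32.5% | 262 |
| 20% | 10.0% | 40.7% | 201 |

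Over all placebo rates, power peaks at 70%, near a rate of 63%. At a 5% placebo rate, even no Fisetin events at all gives only 52% power. To reach 80% with 75 per arm, the rates would have to be about 10% vs 0.7% (OR about 16), 15% vs 2.8% (OR about 6) or 20% vs 5.4% (OR about 4.4).

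**3. If the score governs.** At N = 150, power = Φ[√(150 (1 − Σp̄ᵢ³)/12) × ln 2.24 − 1.960]. The 7 × 2 chi-square column comes from simulation (40,000 trials) of the same distributions. Where 70% are in the best category, the remaining 30% are split equally over six categories, giving 75 × 0.05 = 3.75 expected placebo patients in each, so that chi-square figure is approximate.

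| Placebo distribution (assumed) | 1 − Σp̄ᵢ³ | Proportional-odds power | 7 × 2 chi-square power |
|---|---|---|---|
| Seven equal categories | 0.976 | 80% | about 50% |
| 70% in best, rest equal | 0.544 | 56% | about 24% |
| 85% in best, rest equal | 0.299 | 34% | not relied on (cells too small) |

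Simulated rank tests agree with the proportional-odds column: 0.798, 0.539 and 0.320.

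**The case against.** The best defence has four parts.

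- **The 80% is not a miscalculation.** This stands. The figure is sound for the ordinal model under a near-even spread. The fault is that Sections 5.1 and 8.2.1 describe something else.
- **Section 8.2.1 permits logistic regression.** It does, but only as a possible addition to the chi-square test, and the model is not called ordinal. It does not make the powered model primary.
- **The endpoints might be linked, and the DSMB charter may settle the matter.** The synopsis and Section 2 cite Appendix A for the scale. Appendix A as available lists no categories, possibly because of how the text was extracted, so it cannot be checked whether the composite is a cut of the scale. No section says that it is. The charter was not available. Even if it names one endpoint, the protocol would still contradict itself.
- **This is a pilot.** The plan nevertheless sets a reduced final alpha, efficacy stopping and conditional-power futility, each of which needs one defined endpoint and test.

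Two cautions also stand. That the endpoint could be chosen late is a risk, not something the documents show to be intended. And adopting the Day 30 score matches the method in the power statement but does not by itself secure 80%, as the skewed distributions above show.

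**Conclusion.** The concern holds. The protocol gives two primary endpoints with no order of precedence, and its chi-square test is not the analysis behind its power statement. This can be read from the text without calculation.

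The conclusion for the composite does not depend on which placebo rate is assumed: with 75 per arm and OR 2.24, power never exceeds about 70%, and it is 13% to 41% for placebo rates of 5% to 20%. For the score, 80% requires a proportional-odds test and a nearly even spread of patients over seven categories. Testing the score by a 7 × 2 chi-square test lowers power to about 50% even then. The ordinal figures rest on proportional odds and the assumed distributions. This must be fixed before any unblinded efficacy analysis.

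**What to change.** Before any unblinded efficacy look, name one primary endpoint, one time point and one test, and word them identically in the synopsis and Sections 1.1, 2, 5.1, 8.1, 8.2.1 and 8.2.3. Make the other endpoint the first secondary, and align the secondary lists in the synopsis and Section 5.1 at the same time.

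- **Score at Day 30.** This is the option the power statement names. Replace the chi-square test in the synopsis and Section 8.2.1 with a proportional-odds test, and make sure the seven categories are written out in the protocol.
- **Composite.** Keep the chi-square test, and restate sample size and power for a stated placebo rate.
- **Worst score through Day 30.** Define it on status after randomization only, leaving out the Day 0 score. Add a rule that assigns a category to events arising between scheduled contacts; Appendix B, Section 3.6 already captures these: "Study endpoints are to be reported in the eCRF within 24 hours of awareness of the event".

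In every case, restate power for the chosen endpoint and test, show the assumed event rate or category distribution, and give the DSMB the same endpoint for the interim look.

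The cost is a protocol amendment, matching SAP wording and one power calculation. The restated power may be less favourable than 80%. The worst-score option also needs the between-contact rule.

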5.2 Safety Monitoring

Drug safety will be assessed by an evaluation of types, frequencies, severities and duration of any reported AEs. Patients will be monitored for signs and symptoms of drug toxicity.

For all toxicities that require the study therapy to be temporarily or permanently discontinued, relevant clinical and laboratory tests will be repeated as clinically needed until there is final resolution, stabilization of the toxicity, or another cause for the abnormality is determined.

5.2.1 Adverse Event Reporting

Information regarding AEs will be collected from the first dose of study medication (at Visit 2) through and including the last visit. Any AEs prior to randomization will be recorded in the medical history and kept in the patients' chart.

In addition to standard reporting of Serious Adverse Events (SAEs) as defined and outlined in Section 5.2.1.1 below, information regarding SAEs that occur within 30 days following the last study visit, and reported to the investigational site, will be collected. Each patient will be observed and queried in a non-specific fashion at each visit during the study for any new or continuing symptoms since the previous visit.

All SAEs will be recorded on the appropriate eCRF section. The only other AEs to be recorded on the eCRF are those that are either related to the gastrointestinal system, that are judged related to the study medication by the investigator or laboratory abnormalities judged clinically significant by the investigator. Information collected will include the onset, duration, severity, relationship to study drug, and the management as outlined in Appendix C.

5.2.1.1 Serious Adverse Events

Serious Adverse Events (SAE) are those that meet any of the following International Council for Harmonisation (ICH) criteria:

- Is fatal or immediately life-threatening;
- Results in persistent or significant disability/incapacity;
- Requires or prolongs inpatient hospitalization;
- Is a congenital anomaly/birth defect in the offspring of the patient;
- Is a cancer:
- Is an overdose (intentional or accidental);
- Is judged to be medically important.

Medically important events may not be immediately life-threatening or result in death or hospitalization but may jeopardize the patient or may require intervention to prevent one of the outcomes listed in the definition above. Serious Adverse Events are to be reported if they are known to occur within 30 days following the last study visit.

Medical and scientific judgment should be exercised in deciding whether other AEs meet these criteria and are immediately reportable to the sponsor or designee.

In the event of a serious or life-threatening adverse event, or in the event of death, immediately report the event on the appropriate SAE form in the eCRF.

If any SAE occurs, the study treatment may be interrupted or discontinued at the Investigator's discretion. If an acute medical emergency occurs, the investigator should make every effort to reach the contact person listed above, before breaking the randomization code, via the automated Interactive Web Response System (IWRS). However, the investigator may break the randomization code (via IWRS) at any time if this is required for proper treatment of the patient and even if the contact person could not be reached.

Reports to the Health Authorities must be made within 7 calendar days, (for death and life-threatening events) and within 15 calendar days (for other serious events) after being informed of

an SAE by the investigator.

5.2.1.2 Lack of Efficacy of study medication

Any signs or symptoms defined in the protocol as lack of efficacy or collected as efficacy parameters (endpoints) will be captured as AE in the database.

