8.2.2 Analysis of safety outcomes

Safety of Fisetin will be evaluated by presenting descriptive statistics for various safety endpoints broken down by group. This will be done for the population of patients who received at least one dose of study medication (safety population).

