1.4 Serious Adverse Event (SAE)

Serious Adverse Events (SAE) are those that meet any of the following International Council for Harmonisation (ICH) criteria:

- Is fatal or immediately life-threatening (NOTE: the term "Life-Threatening" refers to an event in which the patient was at immediate risk of death at the time of the event; it does not refer to an event which could hypothetically have caused death had it been more severe);
- Results in persistent or significant disability/incapacity;
- Requires or prolongs patient hospitalization;
- Is a congenital anomaly/birth defect in the offspring of the patient;
- Is a cancer;
- Is an overdose (intentional or accidental);
- Is judged to be medically important.

Medically important events may not be immediately life-threatening, result in death or hospitalization, but may jeopardize the patient or may require intervention to prevent one of the outcomes listed in the definition above. Serious adverse events are to be reported if they are known to occur within 30 days following the last study visit.

Medical and scientific judgment should be exercised in deciding whether other AEs meet these criteria and are immediately reportable to the sponsor or its designee.

Version 4.0, 18NOV2021

Hospitalization is defined as a patient admission to a hospital for medical treatment or observation; a visit to the emergency room for an outpatient consultation is not considered a hospitalization. Moreover, the following hospitalizations are not considered SAEs:

- Hospitalizations for diagnostic or elective surgical procedures for a preexisting condition.
- Hospitalization for therapy of the target disease(s) of the study if the protocol explicitly anticipated and defined the symptoms or episodes.
- Hospitalization for study efficacy measurement, as defined in the protocol.

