3.2 Lack of Efficacy of Study Medication

Signs or symptoms defined in the protocol as lack of efficacy or collected as efficacy parameters (endpoints) will be captured as AEs.

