3.4 Hospitalization or Surgery/Procedure

Any AE reported as study endpoint should not be reported as an SAE. Any condition/diagnosis responsible for surgery/procedure should be reported as an AE if it meets the criteria for an AE. A medical procedure is not considered and should not be reported as an AE. The surgery/procedure itself will be reported as a Clinical Outcome of the underlying event. Events that prolong any hospitalization are reported as SAEs.

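### Efficacy endpoints are captured as adverse events and Section 8.2.2 does not separate them, so adverse event totals by arm mix COVID-19 progression with possible drug toxicity

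*Combined protocol and SAP*

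**What the plan says.** **Capture.** Section 5.2.1.2 directs that signs or symptoms counted as lack of efficacy or "collected as efficacy parameters (endpoints) will be captured as AE in the database". Appendix B 3.2 says the same: "Signs or symptoms defined in the protocol as lack of efficacy or collected as efficacy parameters (endpoints) will be captured as AEs". Appendix B 3.5 makes the cause of death an AE.

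**What else is in the AE data.** Section 5.2.1 and Appendix B 3.6 restrict the other recorded AEs to SAEs, gastrointestinal events, events judged drug-related, and laboratory abnormalities judged clinically significant.

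**Safety analysis.** Section 5.2 bases the safety assessment on the type, frequency, severity and duration of all reported AEs, with no exception for endpoints. The substance of Section 8.2.2 is that "Safety of Fisetin will be evaluated by presenting descriptive statistics for various safety endpoints broken down by group", in patients who took at least one dose. It does not define those endpoints or mention efficacy events.

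**Serious events.** Section 5.2.1.1 lists fatal events and inpatient hospitalization as SAEs without an endpoint exception and adds: "in the event of death, immediately report the event on the appropriate SAE form in the eCRF". Appendix B 3.4 says "Any AE reported as study endpoint should not be reported as an SAE". Appendix B 1.4 lists among hospitalizations that are not SAEs: "Hospitalization for therapy of the target disease(s) of the study if the protocol explicitly anticipated and defined the symptoms or episodes".

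**The concern.** Safety and tolerability is the secondary objective (Section 2), with 75 patients planned on Fisetin. Most ordinary background AEs are never recorded, so endpoint events could be a substantial share of a small AE data set.

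The endpoint events are also the events that the drug is meant to reduce. If it does, AE totals and severity counts on Fisetin fall for a reason unrelated to tolerability and can offset a real excess of other events. The same reduction would then be read twice: once as efficacy and once as good safety.

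The SAE rules do not settle the matter. Whether a COVID-19 death or hospitalization appears in an SAE table depends on which part of the protocol the site follows.

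**Working it through.** **1. The plan's own figure.** Section 8.1 states 80% power with 75 per arm for an odds ratio of 2.24 on the 7-point score. The Whitehead formula is n per arm = 6(z₀.₉₇₅ + z₀.₈₀)² / [(ln OR)² (1 − Σp̄ᵢ³)]. With seven equally likely categories (an assumption; the plan gives no distribution), n = 6(1.960 + 0.842)² / [0.8065² × (1 − 7/343)] = 73.9. Power at 75 per arm is 80.6%. The stated figure is reproduced under that assumption. It is used here only as the source of the odds ratio.

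**2. Inputs for the illustration.**
- From the plan: 75 per arm and OR 2.24.
- Assumed: all 75 per arm are dosed; endpoint events and other toxicity are independent; the ordinal OR applies to a binary endpoint event; placebo endpoint rate e_P is 3% to 30%; other toxicity (Fisetin vs placebo) is 10% vs 5% or 15% vs 5%.

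**3. Formulas.** Fisetin endpoint rate: e_F = o/(1 + o), where o = [e_P/(1 − e_P)]/2.24. Any-AE rate in an arm = 1 − (1 − toxicity)(1 − endpoint rate). Example at e_P = 10%: o = 0.1111/2.24 = 0.0496, so e_F = 4.73%. Any-AE is 1 − 0.90 × 0.9527 = 14.25% on Fisetin and 1 − 0.95 × 0.90 = 14.50% on placebo.

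**4. Results.** Any-AE rates are Fisetin vs placebo, and differences are in percentage points. The last column is the chance that the observed Fisetin count is no higher than placebo, from two Binomial(75, p) distributions at 10% vs 5% toxicity.

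| e_P | e_F | Any-AE, toxicity 10% vs 5% | Difference (true +5) | Any-AE, toxicity 15% vs 5% | Difference (true +10) | Chance Fisetin no higher |
|---|---|---|---|---|---|---|
| 3% | 1.36% | 11.23% vs 7.85% | +3.4 | 16.16% vs 7.85% | +8.3 | 29% |
| 5% | 2.30% | 12.07% vs 9.75% | +2.3 | 16.95% vs 9.75% | +7.2 | 37% |
| 10% | 4.73% | 14.25% vs 14.50% | −0.2 | 19.02% vs 14.50% | +4.5 | 56% |
| 15% | 7.30% | 16.57% vs 19.25% | −2.7 | 21.21% vs 19.25% | +2.0 | 70% |
| 20% | 10.04% | 19.04% vs 24.00% | −5.0 | 23.53% vs 24.00% | −0.5 | 80% |
| 30% | 16.06% | 24.45% vs 33.50% | −9.0 | 28.65% vs 33.50% | −4.8 | 91% |

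On toxicity alone, the last-column chance would be 15%. At 15% vs 5% toxicity it is 2% on toxicity alone and 26% to 77% on the mixed count for e_P from 10% to 30%.

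**5. Where the excess is lost.** Any-AE rates are equal when (1 − e_F)/(1 − e_P) = (1 − placebo toxicity)/(1 − Fisetin toxicity). At 10% vs 5%, the right side is 0.95/0.90 = 1.0556. The placebo odds are then 0.0556/(1 − 1.0556/2.24) = 0.105, so e_P is about 9.5%. At 15% vs 5%, 0.95/0.85 = 1.1176 gives odds of 0.1176/(1 − 1.1176/2.24) = 0.235, so e_P is about 19%.

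**6. Other toxicity rates.** At 20% vs 10%, a true 10-point excess becomes 7.3, 4.8, 0.0 and −4.2 points at e_P of 5%, 10%, 20% and 30%.

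**7. SAE rules side by side.** For a COVID-19 death in the first 30 days, Section 5.2.1.1 requires the SAE form, whereas Appendix B 3.4 says that an event reported as a study endpoint is not reported as an SAE. For a COVID-19 hospitalization, Section 5.2.1.1 counts it as serious, whereas Appendix B 1.4 excludes it if the protocol anticipated and defined it. Both instructions cannot be followed.

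**The case against.** A reader might infer that no safety summary anywhere removes endpoint events. The documents do not support that: an SAE table built on Appendix B 1.4 and 3.4 would omit them. What remains is that Section 5.2.1.1 contradicts those rules, and that the wording of Appendix B 3.4 still treats endpoint events as AEs.

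A reader might also infer that progression is classed as toxicity. It is not. Appendix B 1.2 defines an AE regardless of causality, and Appendix B 2.4 requires a relatedness category. Gastrointestinal and drug-related events listed on their own lines would stay visible. Section 8.2.2 names no pooled any-AE total, so the masking shown above arises only if totals or overall severity counts are presented. That objection stands, and it limits the point to those counts and to body systems that COVID-19 also affects. Section 5.2 does, however, put frequency and severity at the centre of the assessment, and Section 8.2.2 does not say which table carries the safety conclusion.

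Endpoint events are already partly identifiable: Table 1 has separate rows for endpoints and AEs, and Appendix B 3.6 gives endpoints their own 24-hour entry rule. This makes the fix easier, but it does not tell the analyst to separate them.

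Finally, Section 8.2.3 says that the Data and Safety Monitoring Board (DSMB) "will review unblinded safety data as detailed in the DSMB charter". The charter is not among the documents, so nothing can be said about whether the DSMB sees mixed counts.

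**Conclusion.** The point holds for overall AE frequency and severity counts by arm. Capturing endpoints as AEs is an explicit rule in two places, and the safety analysis does not undo it. The direction of the distortion follows from the rule whenever Fisetin lowers endpoint events. Its size depends on rates that the plan does not give.

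Under the assumptions listed, with 10% vs 5% toxicity, the 5-point excess is reduced at placebo endpoint rates of 3% and 5%, is gone near 10%, and is reversed at 15% to 30%. With 15% vs 5%, it shrinks but persists at 10% to 15% and is lost from about 20%. It would therefore be wrong to infer that a doubled toxicity always disappears or reverses: below about a 10% endpoint rate it does not. Applying the ordinal odds ratio to a binary event is itself an assumption.

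Separately, the SAE rules in Section 5.2.1.1 and Appendix B 1.4 and 3.4 contradict each other on endpoint events. This needs no assumed rates.

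**What to change.** - In Section 5.2.1.2 and Appendix B 3.2, state that efficacy endpoint events are identified as such in the AE data.
- In Section 8.2.2, state that AE summaries by arm are shown excluding endpoint events, as the tolerability comparison, and that endpoint events are shown by arm in a separate table beside them. The second table keeps any drug-caused worsening of COVID-19 visible.
- Say which definition of endpoint event applies, because Section 5.1 uses death or COVID-19 hospitalization while the synopsis and Section 2 use the 7-point score.
- Reconcile Section 5.2.1.1 with Appendix B 1.4 and 3.4 on whether endpoint deaths and hospitalizations are SAEs. Which rule should apply is for the sponsor to decide.

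The cost is a few sentences, one indicator on data already collected, and one extra table. No patients, visits or assessments are added, and no DSMB trigger or stopping rule is proposed.
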